6.4 DOSE REDUCTIONS/ADJUSTMENTS

6.4.1 *OPROZOMIB DOSING DELAYS, MODIFICATIONS, AND REINTRODUCTION*

The dose of oprozomib should be held and/or reduced according to the guidelines described below. Dose reduction should be continued until resolution of toxicity (per [Table 6](#) and [Table 7](#)). Subjects having severe toxicity will be allowed 3 dose reductions in 30 mg increments to a maximum reduction of 90 mg with a minimum dose of 150 mg. A final dose reduction will be managed by reducing dose intensity by schedule, if fewer than 3 dose reductions have occurred and subjects are currently dosed at 150 mg.

- Subjects on the 5/14 schedule who have had fewer than 3 reductions down to a dose of 150 mg may reduce the intensity on the next reduction by changing from 5 to 3 consecutive days for every 14-day cycle.
- Subjects on the 2/7 schedule who have had fewer than 3 reductions down to a dose of 150 mg may reduce the intensity on the next reduction by changing from 2 consecutive doses to 1 day weekly for every 14-day cycle.
- Exceptions to the dose modification guidelines are permitted after written approval from the **Sponsor** study medical monitor.

6.4.1.1 Dose Modification for Hematologic Toxicities

[Table 7](#) summarizes hematologic toxicities and oprozomib dosing actions that should occur in the event of toxicities.

Table 7: Guidelines for Dose Modification for Hematologic Toxicities

Toxicity	Oprozomib Dosing Action
ANC \geq 500 cells/mcL	Continue at full dose
ANC < 500 cells/mcL for less than 7 days	Hold dose. When ANC \geq 500 cells/mcL, resume at full dose.
ANC < 500 cells/mcL for 7 days or longer	Hold dose. When ANC > 500 cells/mcL, resume at 1 dose decrement.
Grade 3 febrile neutropenia	Hold dose. When ANC \geq 1000 cells/mcL and fever has resolved, resume at 1 dose decrement.
Platelet count < 50,000 cells/mcL and \geq 25,000 cells/mcL without evidence of bleeding	Continue at full dose
Platelet count < 50,000 cells/mcL and \geq 25,000 cells/mcL with evidence of bleeding	Hold dose. When platelet count returns to > 50,000 cells/mcL and bleeding stops, resume at 1 dose decrement.
Platelet count < 25,000 cells/mcL for < 7 days without evidence of bleeding	Hold dose. When platelet count \geq 25,000 cells/mcL, resume at full dose.
Platelet count < 25,000 cells/mcL for \geq 7 days with or without evidence of bleeding	Hold dose. When platelet count \geq 25,000 cells/mcL, resume at 1 dose decrement.

ANC = absolute neutrophil count.

Additional guidance regarding hematologic toxicities and dosing actions is as follows:

- Non-treatment-related events: If the toxicity resolves to \leq Grade 1 or baseline and the toxicity is not treatment related, oprozomib may be restarted at the same dose level.
- If required by continued or recurrent toxicity, a second or third dose reduction may be permitted down to a minimum dose of 150 mg after discussion with the **Sponsor** medical monitor. If the subject has not had 3 reductions but is at a dose level of 150 mg, an additional reduction may occur via reducing dose intensity (see [Section 6.4.1](#)). No more than 3 dose reductions will be permitted in an individual subject on study; if toxicity continues, the subject should be removed from the study.
- If the subject tolerates the reduced dose for 1 cycle, the subject's dose may be escalated to the dose prior to the dose reduction.
- If there is no resolution of toxicity after 2 weeks of withholding treatment (up to 3 weeks if an infection is being treated), the subject will be discontinued from the study.

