- Febrile neutropenia: Any single temperature $\geq 38.3^\circ\text{C}$ or a sustained temperature of $\geq 38.0^\circ\text{C}$ for over 1 hour with \geq Grade 3 neutropenia (ANC < 1000 cells/mcL)
- Grade 3/4 thrombocytopenia
 - Grade 3 thrombocytopenia of any duration with Grade 2 bleeding or requiring platelet transfusion
 - Grade 4 lasting ≥ 7 days

- Grade 4 lasting < 7 days with Grade 2 bleeding, or if platelet counts are lower than 10,000 cells/mcL, requiring a platelet transfusion

Note: The following will not be considered a DLT:

- Grade 4 anemia
- Grade 4 thrombocytopenia lasting < 7 days with platelet counts above 10,000 cells/mcL without clinically significant bleeding and with or without transfusion

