6.5 SAFETY GUIDANCE FOR INVESTIGATORS

Based on the experience in nonclinical studies of oprozomib and available Phase 1 clinical data in subjects with solid tumors and hematologic malignancies, the following guidance is recommended but not mandated to investigators unless otherwise noted in the dose reduction guidelines:

- Subjects with active systemic infections of any kind should not be dosed with oprozomib until infection has resolved. Subjects with neutrophil counts related to their infection of $ANC < 500$ cells/mcL should not be treated until the neutrophil count has recovered to > 1500 cells/mcL.
- For platelet counts $< 25,000$ cells/mcL, oprozomib dosing should be held until platelet count is $\geq 25,000$ cells/mcL independent of platelet transfusions for 1 week. Consideration of dose reduction of oprozomib should be given if it is thought that oprozomib may have caused the thrombocytopenia.

- Subjects should have anemia corrected in accordance with the institutional guidelines, which can include transfusions or support with erythropoietin or darbepoetin.
- Based on the high incidence of nausea and vomiting that has been observed to date, it is recommended that subjects treated with oprozomib receive prophylactic antiemetics that would typically be utilized to prevent nausea and vomiting prior to moderately to highly emetogenic therapies.
- Prophylactic treatment for diarrhea is not recommended; however, subjects who experience diarrhea should be treated with antidiarrheals and may be given prophylaxis once they are known to have diarrhea related to administration of oprozomib.
- Hypophosphatemia has been observed in a few subjects treated with oprozomib. Severe hypophosphatemia has also been observed in subjects treated with other proteasome inhibitors, including carfilzomib (data on file), bortezomib (Messinger 2010), and MLN 9708 (Richardson 2012). This typically has been transient and not associated with clinical symptoms. Subjects should be monitored carefully for electrolyte abnormalities, and electrolytes should be replaced as needed.

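### Table 7 gives conflicting restart instructions for a subject still bleeding as platelets recover from below 25,000, and has no row for bleeding in the first 7 days below 25,000

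*Protocol*

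**What the plan says.** Table 7 in Protocol Section 6.4.1.1 has four platelet rows (counts in cells/mcL):

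- **Row A:** 25,000 to under 50,000, no bleeding. Dosing continues at full dose.
- **Row B:** 25,000 to under 50,000, with bleeding. The action is "Hold dose. When platelet count returns to > 50,000 cells/mcL and bleeding stops, resume at 1 dose decrement".
- **Row C:** headed "Platelet count < 25,000 cells/mcL for < 7 days", and limited to subjects who are not bleeding. Hold until the count is at least 25,000, then return to full dose.
- **Row D:** below 25,000 for 7 days or longer, "with or without evidence of bleeding". Hold until the count is at or above the threshold, with the restart given as "25,000 cells/mcL, resume at 1 dose decrement". There is no bleeding condition.

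The bullets under the table add no bleeding condition and no order of precedence. They discontinue a subject whose toxicity has not resolved after 2 weeks of withheld treatment, or 3 weeks if an infection is being treated.

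Three other places bear on the point.

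- Section 6.3 lists as a DLT "Grade 4 lasting < 7 days with Grade 2 bleeding".
- Section 6.5 advises holding at any count below 25,000 until it is back to 25,000 "independent of platelet transfusions for 1 week", and considering a dose reduction. It opens by saying that its "guidance is recommended but not mandated to investigators", and its platelet advice does not mention bleeding.
- Table 8 (Section 6.4.1.2) delays dosing for Grade 1–2 GI hemorrhage until Grade 0, stops it for Grade 3–4 GI hemorrhage, and has general rules for other Grade 3 and Grade 4 nonhematologic events.

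**The concern.** The deeper and longer platelet fall carries the weaker restart condition. Bleeding at 25,000 to under 50,000 needs both a count above 50,000 and an end to bleeding. Bleeding after a week or more below 25,000 needs, on Row D alone, only a count of 25,000. This looks like an omission, because the protocol elsewhere waits for the clinical sign to clear: febrile neutropenia requires the fever to have resolved as well as the neutrophil count to recover, and low-grade GI bleeding must reach Grade 0.

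What is at stake is patient safety. A site that follows Row D literally could redose a subject who is still bleeding. For bleeding early in a fall below 25,000, Table 7 gives the site no hold or restart rule at all.

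The situation is foreseeable. Inclusion criterion 6 admits subjects at 30,000 platelets, close above the 25,000 boundary, and Section 1.4.3 reports Grade 4 thrombocytopenia as a DLT on both schedules. Under Amendment 4 some subjects remain on treatment, blood counts are taken only when clinically indicated and at end of study, and eligible subjects may collect 4 cycles of drug at a time. With fewer scheduled contacts, the written rule matters more.

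**Working it through.** No sample-size or error-rate figure is involved. The check is whether each platelet state below 50,000 leads to exactly one instruction.

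**Inputs.** Rows A to D as described above. States are formed from count (25,000 to under 50,000, or below 25,000), duration (only relevant below 25,000: under 7 days, or 7 days or more) and bleeding (no or yes). That gives 2 + 2 × 2 = 6 states.

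| State | Row | Restart condition | Must bleeding stop? |
|---|---|---|---|
| 25,000 to <50,000, no bleeding | A | none, dosing continues | not applicable |
| 25,000 to <50,000, bleeding | B | >50,000 and bleeding stopped, 1 decrement | yes |
| <25,000, <7 days, no bleeding | C | ≥25,000, full dose | not applicable |
| <25,000, <7 days, bleeding | none | none given | no row |
| <25,000, ≥7 days, no bleeding | D | ≥25,000, 1 decrement | not applicable |
| <25,000, ≥7 days, bleeding | D | ≥25,000, 1 decrement | no |

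**Coverage.** 6 − 1 = 5 of 6 states have a row. Of the 3 bleeding states, 1 requires bleeding to stop, 1 does not, and 1 has no row.

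**Three illustrative subjects.**

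1. *20,000 for 8 days with bleeding, then 30,000 and still bleeding.* At 20,000 only Row D applies, and its restart condition (at least 25,000) is met at 30,000, so it says resume. At 30,000 with bleeding, Row B also describes the subject, and says hold until above 50,000 with bleeding stopped. The instructions are opposite and nothing says which prevails.
2. *20,000 on day 3 with bleeding.* Row C excludes bleeding and Row D needs 7 days, so no row applies. Reading Grade 4 thrombocytopenia as a count below 25,000, the boundary Table 7 uses, this is the state that Section 6.3 calls a DLT when the bleeding is Grade 2.
3. *20,000 for 8 days with bleeding that stops before the count reaches 25,000.* Only Row D applies: restart one decrement lower at 25,000. There is no conflict, and nothing here needs changing.

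**Does other text settle subjects 1 and 2?** Section 6.5 supports a hold for subject 2, but only as advice; it does not make restart depend on bleeding and leaves dose reduction to consideration. Table 8 settles both cases if the bleeding is GI, and gives a hold or stop if it is another Grade 3 or Grade 4 nonhematologic event. What remains is mainly Grade 1–2 bleeding outside the GI tract. The medical monitor may approve exceptions in writing (Section 6.4.1), but that supplies no default rule.

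**After the change described under the fix.** 6 of 6 states have a row and 3 of 3 bleeding states require bleeding to stop. Subjects 1 and 2 each get one instruction, and subject 3 is unchanged. These are counts of table cells and do not measure risk.

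**The case against.** The strongest reply is that Table 7 does not simply permit dosing during bleeding. A subject bleeding at 30,000 fits Row B exactly, and Row B orders a hold; a careful site would apply the row for the subject's current state. This stands. A reader might infer from Row D alone that the protocol authorizes restart in a bleeding subject, but the documents support only a conflict between two rows with no stated precedence.

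The missing row is also narrower than it first appears. Both printed rows below 25,000 say hold, Section 6.5 advises the same, Row D applies from day 7, and Row B applies if bleeding continues once the count reaches 25,000. What is truly open is a mandatory hold and the restart dose (full, or one decrement down) when bleeding stops before 25,000. This also stands, and it is why the gap is secondary. The DLT listing has limited weight for subjects still on treatment, because it concerns the Phase 1b assessment period.

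A reader might try to use the 2-week discontinuation rule to limit the conflict to a set number of days. The documents do not support that. The rule counts weeks of withheld treatment, and on the 5/14 schedule oprozomib is given only on Days 1 to 5, so a fall after Day 5 may withhold nothing until the next cycle.

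Nor do the subarachnoid hemorrhage in this study or the fatal GI bleeds in Study 2011-001 show harm from this rule. The documents do not link them to low platelets or to a restart under Table 7.

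Many clinicians would hold a bleeding subject whatever the table says. That reduces the practical effect but does not make the written rule consistent.

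**Conclusion.** The point holds as a drafting conflict with a safety consequence. For a subject who bled below 25,000 for 7 days or more and is still bleeding at 25,000 to under 50,000, one Table 7 row says resume, another says hold, and neither is given priority. Secondarily, bleeding in the first 7 days below 25,000 has no row.

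The size is 1 of 6 states without a row and 1 of 3 bleeding states with a requirement that bleeding stop. The documents give no count of Grade 1–2 non-GI bleeding below 25,000, so the number of subjects affected is unknown. It is probably small, because Table 8 covers GI hemorrhage and Grade 3–4 events. No limit in days is claimed.

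The conclusion assumes that Grade 4 thrombocytopenia means a count below 25,000 and that Table 7 is read literally. It should be corrected, because following one stated rule to the letter could redose a bleeding subject and the repair is short.

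**What to change.** Make two changes to Table 7.

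1. **Row D (below 25,000 for 7 days or more).** Keep the hold and the restart one decrement down at 25,000, but only if any bleeding has already stopped. Add that a subject still bleeding at 25,000 to under 50,000 follows the existing bleeding row for that range, and so stays on hold until the count exceeds 50,000 and bleeding has stopped.
2. **New row: below 25,000 for under 7 days, with bleeding.** Give it the same action as the revised Row D, including the cross-reference.

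Putting the cross-reference inside the row matters. If bleeding continues past 25,000 and then stops at, say, 35,000, the subject has one instruction: wait until above 50,000.

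The cost is a protocol amendment with IRB/IEC approval (Section 12.2) and some longer holds. Subjects still bleeding on reaching 25,000 must exceed 50,000, as Row B already says. That includes those who entered at 30,000 to 50,000, who would have to exceed their entry count. Those who do not recover may be discontinued under the existing 2-week rule (3 weeks with a treated infection), if continued bleeding or a low count is taken as unresolved toxicity. Subjects whose bleeding stops before 25,000 restart at 25,000 as under the present Row D. One asymmetry remains: a subject who bled only at 26,000 must still exceed 50,000. No platelet threshold is altered, and alpha, power and sample size are unaffected.

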6.4.1.2 Dose Reduction for Nonhematologic Toxicities

[Table 8](#) summarizes nonhematologic toxicities and oprozomib dosing actions that should occur in the event of toxicities.

Table 8: Guidelines for Dose Modification for Nonhematologic Toxicities

Toxicity	Oprozomib Dosing Action
Tumor Lysis Syndrome, defined as abnormalities in at least 3 of the following 4 categories: (1) Increase in creatinine, uric acid, phosphate of $\geq 50\%$ (2) Increase in potassium of $\geq 30\%$ (3) Decrease in calcium of $\geq 20\%$, or (4) Increase in LDH ≥ 2 -fold from baseline	Hold oprozomib until all abnormalities in serum chemistries have resolved to baseline, then resume at full doses.
Grade 3 nonhematologic toxicity	Hold dose until toxicity resolved to \leq Grade 1 or has returned to baseline. Resume study drug at 1 dose decrement.
Grade 4 nonhematologic toxicity	Discontinue dosing.
Grade 2 neuropathy with pain or \geq Grade 3 neuropathy	Hold dose until toxicity resolved to \leq Grade 1 or has returned to baseline. Resume study drug at 1 dose decrement.
Grade 3 nausea, vomiting, diarrhea and/or constipation without optimal supportive care	Continue dosing, but administer optimal supportive care.
Grade 3 nausea, vomiting, diarrhea and/or constipation with optimal supportive care	Hold dose until toxicity resolved to \leq Grade 1 or has returned to baseline. Resume study drug at 1 dose decrement.
Grade 3 fatigue lasting < 14 days	Continue dosing.
Grade 3 fatigue lasting \geq 14 days	Hold dose until toxicity has resolved to \leq Grade 1 or has returned to baseline. Resume study drug at 1 dose decrement.
Grade 1 or 2 GI hemorrhage	DELAY until Grade 0 DECREASE one dose level for Grade 2
Grades 3 or 4 GI hemorrhage	Discontinue dosing

GI = gastrointestinal; LDH = lactate dehydrogenase.

Additional guidance regarding nonhematologic toxicities and dosing actions is as follows:

- Non-treatment-related events: If the toxicity resolves to \leq Grade 1 or baseline and the toxicity is not treatment-related, oprozomib may be restarted at the same dose level.
- If required by continued or recurrent toxicity, a second or third dose reduction down to a minimum of 150 mg may be permitted after discussion with the **Sponsor** medical monitor. If the subject has not had 3 reductions but is at a dose level of 150 mg, an additional reduction may occur via reducing dose intensity (see [Section 6.4.1](#)). No more than 3 dose reductions will be permitted in an individual subject on study; if toxicity continues, the subject should be removed from the study.
- If the subject tolerates the reduced dose for 1 cycle, the subject's dose may be escalated

to the dose prior to the dose reduction.

- If there is no resolution of toxicity after 2 weeks of withholding treatment (up to 3 weeks for infection treatment), the subject will be discontinued from the study.
- Subjects with Grade 3 or 4 GI hemorrhage should not be rechallenged. Oprozomib should be permanently discontinued. Endoscopy should be considered for all subjects who develop GI hemorrhage.

6.4.1.3 Infections

Subjects with active systemic infections of any kind should have dosing withheld until the infection has resolved. After the infection has resolved, treatment may continue at the original dose. If there is no resolution of infection after 3 weeks, the subject will be discontinued from the study.

6.4.1.4 Congestive Heart Failure

Acute development or exacerbation of CHF or new onset of decreased left ventricular ejection fraction in a subject (as defined by an increase of NCI-CTCAE ≥ 1 grade from baseline), whether or not drug related, requires withholding of the dose until resolution. After the CHF has resolved or returned to baseline, treatment may continue at a dose reduced by 30 mg, with the approval of the **Sponsor** medical monitor, or the subject may be discontinued from the study. If there is no resolution of CHF after 2 weeks, the subject will be discontinued from the study.

6.4.1.5 Conditions Not Requiring Dose Reduction

The following conditions are exceptions to the above guidelines. Oprozomib does not need to be held or dose reduced in the following cases:

- Grade 3 nausea, vomiting, constipation, or diarrhea (unless persisting despite optimal treatment with antiemetics or antidiarrheals)
- Grade 3 fatigue (unless persisting for > 14 days)
- Asymptomatic Grade 3 hypophosphatemia lasting less than 24 hours

6.4.1.6 Dosing Delays

Dosing delays are not permitted in the DLT assessment period. If the timing of later cycles must be adjusted for reasons unrelated to toxicity (e.g., holidays or subject requests), the cycle must be started no sooner than 1 day before or no later than 14 days after the originally scheduled

next cycle, unless permission is granted by the medical monitor. If subjects miss more than 4 weeks of oprozomib, they will be restarted at 150 mg for the 5/14 schedule or 240 mg for the 2/7 schedule using the step-up dose scheme with 1 cycle at the dose level described for each schedule, and then step-up to their last dose level prior to the therapy hold. Schedule adjustments may be made only at the beginning of each cycle; and adjustments may not be made mid-cycle. If possible, future cycles should revert back to the original day of dosing for the schedule.

6.4.2 *DEXAMETHASONE: DOSING DELAYS, MODIFICATIONS, AND REINTRODUCTION*

Guidelines for dexamethasone dose modifications are summarized in [Table 9](#). In the event oprozomib is permanently discontinued, dexamethasone should also be discontinued (refer to [Section 8](#)).

Table 9: Treatment Guidelines for Dexamethasone-related Toxicity

Body System	Symptom	Recommended Action
Gastrointestinal	Dyspepsia, gastric or duodenal ulcer, or gastritis Grades 1 and 2 (requiring medical management)	Continue dexamethasone at same dose and treat with therapeutic doses of H ₂ blockers or proton pump inhibitor. May consider adding sucralfate or other anti-ulcer treatment as clinically indicated. If symptoms persist despite above measures, decrease dexamethasone dose by 1 dose level.
Gastrointestinal	Dyspepsia, gastric or duodenal ulcer, or gastritis ≥ Grade 3 (requiring hospitalization or surgery)	Hold dexamethasone until symptoms return to baseline. Restart dexamethasone at 1 dose decrement along with concurrent therapy with H ₂ blockers, sucralfate, or omeprazole. If symptoms persist despite above measures, discontinue dexamethasone permanently.
Gastrointestinal	Acute pancreatitis	Discontinue dexamethasone permanently.
General disorders	Edema ≥ Grade 3 (≥ 30% limb discrepancy in volume; gross deviation from normal anatomic contour; limiting self-care ADL)	Hold dexamethasone until symptoms return to baseline. Give diuretics as needed, and restart dexamethasone at 1 dose decrement; if edema persists despite above measures, decrease dose another level. Discontinue dexamethasone permanently if symptoms persist despite second reduction.
Psychiatric Disorders	Confusion or mood alteration ≥ Grade 2 (interfering with function ± interfering with ADL)	Hold dexamethasone until symptoms return to baseline. Restart dexamethasone at 1 dose decrement. If symptoms persist despite above measures, reduce by another dose decrement.
Musculoskeletal	Muscle weakness ≥ Grade 2 (symptomatic and interfering with function ± interfering with ADL)	Hold dexamethasone until symptoms return to baseline. Restart dexamethasone at 1 dose decrement. If weakness persists, decrease dose by 1 more dose level. Discontinue dexamethasone permanently if symptoms persist.
Metabolism and Nutrition Disorders	Hyperglycemia ≥ Grade 3 (fasting glucose > 250 mg/dL)	Hold dexamethasone until glucose is ≤ Grade 2 (< 250 mg/dL) and treat with insulin or other hypoglycemic agents as needed. If uncontrolled despite above measures, decrease dose by 1 dose level until ≤ Grade 2 (< 250 mg/dL)
All Other	Other nonhematologic toxicity ≥ Grade 3 considered related to dexamethasone	Hold dexamethasone dose. Resume at 1 dose decrement when toxicity has resolved to Grade 2 or less or to baseline. If toxicity recurs, hold dexamethasone dose until toxicity has resolved to Grade 2 or less or to baseline, and resume dexamethasone dose by 1 more dose decrement. If toxicity recurs despite 2 dose decrements, discontinue dexamethasone permanently.

ADL = activities of daily living.

Two dose-reduction levels are defined for dexamethasone, as illustrated in [Table 10](#).

Table 10: Dose Decrements for Dexamethasone

Nominal Dose	Reduced Dexamethasone Doses	
	Dose -1	Dose -2
20 mg	12 mg	8 mg

Dexamethasone will be permanently discontinued after 2 dose reductions in the event of an additional dexamethasone-related DLT. At the investigator's discretion, dexamethasone dosing may be tapered prior to complete discontinuation, according to institutional practice. If the dexamethasone dose is reduced during the previous cycle, the lower dose level will be continued on Day 1 of the new cycle. If the reduced dose level is well tolerated for a complete cycle, the subject may, at the investigator's discretion, be rechallenged at the start of the next cycle with the dose level given prior to the reduction. If myeloma treatment doses of dexamethasone as noted in [Table 9](#) are discontinued, antiemetic doses of dexamethasone, generally considered to be 4 mg on the days of dosing, may be continued if tolerable per investigator discretion.

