Response rates for subjects with multiple myeloma (n = 43) and subjects with Waldenström macroglobulinemia (WM; n = 18) by schedule and formulation are summarized in [Table 1](#) and [Table 2](#).

Table 1: Phase 1 Response Rates for Subjects with Multiple Myeloma by Schedule and Formulation

Formulation/Schedule (n)	Dose Range (mg)	ORR (≥ PR)	Clinical Benefit Rate (≥ MR)
PIC 5/14 (10)	120–210	40%	50%
Tablets 5/14 (18)	150–270	27.8%	38.9%
Tablets 2/7 (15)	150–330	20.0%	46.7%

ORR = overall response rate; PIC = powder in capsule.

Table 2: Phase 1 Response Rates for Subjects with Waldenström Macroglobulinemia by Schedule and Formulation

Formulation/Schedule (n)	Dose Range (mg)	ORR (≥ MR)	Major Response (≥ PR)
Tablets 5/14 (11)	150–270	63.6%	54.5%
Tablets 2/7 (7)	150–330	42.9%	14.3%

ORR = overall response rate; PIC = powder in capsule.

The Phase 2 portion of Study 2011-001 is ongoing. Eight response-evaluable subjects have received Oprozomib Tablets on the 5 consecutive day bimonthly schedule with once daily dosing in Phase 2; 7 subjects had SD, and 1 subject was off study prior to any disease response assessment.

1.4.3 *STUDY 2012-001: OPROZOMIB IN COMBINATION WITH DEXAMETHASONE IN MULTIPLE MYELOMA*

2012-001 is the study on which this protocol amendment is based. See [Section 3.1](#) for information on study methodology.

Safety

The 2012-001 Phase 1b/2 study assessing safety and activity of Oprozomib Tablets in combination with dexamethasone is currently enrolling in the Phase 1b portion of the study.

- As of May 2014, 12 subjects have been enrolled and treated at doses of 180 mg (n = 5) to 210 mg (n = 7) on the 5/14 schedule, and 4 subjects remain on study. Three

subjects have experienced DLTs at the 210 mg dose, including 1 subject with a subarachnoid hemorrhage, 1 subject with Grade 3 transaminitis, and 1 subject with Grade 4 thrombocytopenia. In addition, 1 subject had 3 SAEs (esophagitis, urinary tract infection, and pneumonia).

- As of May 2014, 13 subjects have been enrolled and treated at doses of 180 mg (n = 3), 210 mg (n = 3), 240 mg (n = 3), to 270 mg (n = 4) on the 2/7 schedule, and 7 subjects remain on study. One DLT of Grade 4 thrombocytopenia has been observed.

Efficacy

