NA	404 ^b	360	20

CSRC = Cohort Safety Review Committee; DLT = dose-limiting toxicity; MTD = maximum tolerated dose; NA = not applicable.

Note: This table is for illustrative purposes.

^a If DLTs are observed in 2 or more subjects at the first dose level of 210 mg, dosing of Cohort -301 or -401 will proceed at 180 mg, or a lower dose as agreed with the CSRC and sponsor, and may be expanded up to 6 evaluable subjects.

^b Additionally, subsequent cohorts of 3 subjects will continue to be enrolled with doses escalated by 30 mg until the MTD (the highest dose at which a DLT is observed in fewer than 2 of 6 evaluable subjects) is defined.

Table 4: Dose-Escalation Schemes Using Oprozomib Extended Release Tablets: 5 Consecutive Day Bimonthly Schedule

5 Consecutive Day Bimonthly Schedule	Oprozomib Daily Dose Cycle 1 (mg)	Oprozomib Daily Dose to be Studied Cycles 2+ (mg)	Dexamethasone Dose (mg)
Step-up dosing with initial 1 cycle of 150 mg			
501 ^a	150	180	20
Continuous dosing			
502	180	180	20
Step-up dosing with initial 1 cycle of 150 mg			
503	150	210	20
504	150	240	20
505	150	270	20

^a Cohort will be dosed at 150 mg for 1 cycle and then increased to the step-up dose to be studied on Cycle 2 for the 5/14 once-daily dosing schedule. This is just an example and not meant to be all encompassing for further dose escalation beyond 270 mg. Dose-limiting toxicity period will be 1 cycle (Cycle 1 for continuous dosing or Cycle 2 for step-up dosing).

**Table 5: Dose-Escalation Schemes for Oprozomib Extended Release Tablets:
2 Consecutive Day Weekly Schedule**

2 Consecutive Day Weekly Schedule	Oprozomib Daily Dose Cycle 1 (mg)	Oprozomib Daily Dose to be Studied Cycles 2+ (mg)	Dexamethasone Dose (mg)
Cohort for continuous dosing			
601 Repeat at continuous dosing MTD ^b unless MTD achieved with OPZ ER Tablets	MTD	MTD ^b	20
Step-up dosing with initial 1 cycle 240 mg ^a			
602	240	MTD ^b	20
603	240	MTD ^b + 30	20
604	240	MTD ^b + 60	20
605	240	MTD ^b + 90	20

^a Cohorts will be dosed at 240 mg for 1 cycle and then increased to the step-up dose to be studied on Cycle 2 for the 2/7 once-daily dosing schedule. Dose-limiting toxicity period will be 1 cycle (Cycle 1 for continuous dosing or Cycle 2 for step-up dosing).

^b MTD for continuous dosing is to be determined.

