6.2.2 DOSE-ESCALATION RULES

The planned and contingent dose levels are provided in Section 3.1.2 (Table 3, Table 4, and Table 5), and dose escalation rules are provided in Table 6. Additional details can be found in the Cohort Management Plan.

Table 6: Dose-Escalation Rules

No. of Evaluable Subjects with Treatment-related DLT at a Given Dose Level	Dose Escalation Rules
0 of 3	Next cohort of 3 subjects treated at the next planned higher dose level.
1 of 3	Up to 3 more subjects are treated at that same dose level.
≥ 2 of 3	Dose escalation stops. Three more subjects will be added to the next lower dose level, unless 6 subjects have already been treated at that dose level.
1 of 6	Next cohort of 3 subjects treated at the next planned higher dose level.
≥ 2 of 6	Dose escalation stops. Additional subjects may be treated at the next lower dose level, for a minimum of 6 subjects treated at that dose level.
Highest dose with < 2 of 6	Maximum tolerated dose

Source: Modified from Simon 1997.

DLT = Dose-limiting toxicity.

Intrasubject dose escalation to the recommended Phase 2 dose may be permitted once that dose has been determined and after discussion between the treating physician and the **Sponsor** medical monitor.

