6.4.3 MISSED DOSES

Subjects must receive all planned doses in the DLT assessment period in order to be assessed for DLT in Phase 1. Planned doses that are missed can be made up if they are received within the same calendar day of scheduled administration. If a subject misses more than 2 consecutive cycles after completing the DLT assessment period for reasons other than toxicity, the subject will be discontinued unless it is determined that the subject was benefiting from therapy and that the medical monitor permits the subject to resume therapy. See [Section 6.4.1.6](#) for information on cycle delays.

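### On the 2/7 schedule, the restart after more than 4 missed weeks is fixed at 240 mg with no cap at the last dose, so subjects last on 150 to 210 mg restart at a higher dose

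*Protocol*

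**What the plan says.** Protocol Section 6.4.1.6 covers any subject whose gap in oprozomib dosing exceeds 4 weeks, and its instruction reads: "they will be restarted at 150 mg for the 5/14 schedule or 240 mg for the 2/7 schedule using the step-up dose scheme". The first dose is given for one cycle "and then step-up to their last dose level prior to the therapy hold". The rule sets no condition on what the last dose was.

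Other sections show that 2/7 subjects can be below 240 mg:

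- Section 6.4.1 allows up to three reductions of 30 mg with a floor of 150 mg, and it addresses 2/7 subjects at that floor directly: "Subjects on the 2/7 schedule who have had fewer than 3 reductions down to a dose of 150 mg may reduce the intensity".
- Section 3.1.2, Table 3, lists 2/7 cohorts at 210 mg and 180 mg. Footnote a says that if the first level is too toxic, "dosing of Cohort -301 or -401 will proceed at 180 mg, or a lower dose as agreed with the CSRC and sponsor".
- Section 1.4.3 reports that by May 2014, on 2/7, "13 subjects have been enrolled and treated at doses of 180 mg (n = 3), 210 mg (n = 3), 240 mg" and 270 mg.
- Section 1.5.1 keeps subjects at the same dose when they switch to ER tablets, so the switch does not bring anyone up to 240 mg.

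Two rules limit dose increases within a subject. Sections 6.4.1.1 and 6.4.1.2 allow a return to the dose before a reduction on the condition "If the subject tolerates the reduced dose for 1 cycle". Section 6.2.2 says "Intrasubject dose escalation to the recommended Phase 2 dose may be permitted once that dose has been determined", after discussion with the medical monitor.

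**The concern.** The purpose of the restart rule is to bring a subject back gently after a long gap: one cycle at a lower dose, then the previous dose. On 2/7 it does this only if the previous dose was above 240 mg. For a subject last on 150, 180 or 210 mg, the written instruction raises the dose on re-exposure and lowers it one cycle later.

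It can also override the two limits on increases. A subject reduced for toxicity can be put back above the reduced dose without having tolerated it for a cycle. A subject assigned to a low cohort can be escalated to a dose that is not the recommended Phase 2 dose.

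What is at stake is the safety of individual subjects. The worst case is someone reduced for toxicity to the 150 mg floor. Under Amendment 4, the appendix footnotes make most vital signs, chemistry and blood counts for subjects still on treatment dependent on clinical need, so an unintended increase may be watched less closely.

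**Working it through.** **Inputs.** Restart dose on 2/7: 240 mg (Section 6.4.1.6). Reductions: up to 3 of 30 mg, floor 150 mg (Section 6.4.1). 2/7 dose levels: 180, 210, 240, 270, 300, 330 and 360 mg (Table 3, marked as illustrative). Dosing days per cycle on 2/7: 4 (Days 1, 2, 8 and 9). The plan gives no figure of its own to reproduce on this point.

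**Step 1: increase at restart.** Increase = 240 − last dose, and the cycle total is 4 × dose.

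| Last dose | Increase per dose | Ratio | Restart cycle vs last-dose cycle | Extra per cycle |
|---|---|---|---|---|
| 210 mg | 30 mg | 240/210 = 1.14 | 960 vs 840 mg | 120 mg |
| 180 mg | 60 mg | 240/180 = 1.33 | 960 vs 720 mg | 240 mg |
| 150 mg | 90 mg | 240/150 = 1.60 | 960 vs 600 mg | 360 mg |

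**Step 2: where last doses below 240 mg come from.** Apply 0 to 3 reductions to each level and keep the doses under 240 mg.

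| Starting level | Reachable doses below 240 mg |
|---|---|
| 180 mg | 180, 150 |
| 210 mg | 210, 180, 150 |
| 240 mg | 210, 180, 150 |
| 270 mg | 210, 180 |
| 300 mg | 210 |
| 330 mg | none (lowest 240) |
| 360 mg | none (lowest 270) |

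This gives 5 of 7 levels.

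**Step 3: the 5/14 schedule.** The restart dose is 150 mg, which equals the reduction floor. For last doses of 150, 180 and 210 mg the difference is 0, −30 and −60 mg, so the restart is never an increase. This assumes that no 5/14 cohort is opened below 150 mg, and none is listed.

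**Step 4: how many subjects.** In May 2014 there were 3 + 3 = 6 subjects of 13 in 2/7 cohorts below 240 mg and 3 + 4 = 7 at 240 or 270 mg. Seven of the 13 remained on study. All 7 could be from the higher cohorts, or up to 6 from the lower ones, so between 0 and 6 of those remaining came from the lower cohorts. Subjects reduced below 240 mg from a higher cohort are not counted here, and the documents give no number for them.

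**The case against.** The strongest reply is that almost nobody reaches this rule without an individual decision. Unresolved toxicity means discontinuation after 2 weeks, or 3 weeks for infection. Two 14-day cycles are 4 weeks, so the restart threshold nearly coincides with Section 6.4.3. Under that section, a subject missing more than 2 consecutive cycles for reasons other than toxicity is discontinued unless benefiting and "the medical monitor permits the subject to resume therapy". Section 6.4.1 also lets the monitor approve exceptions to the dose guidelines in writing. All of this stands, and it makes the event rare. But Section 6.4.3 settles whether treatment resumes, and Section 6.4.1.6 then prescribes the dose. The exception clause makes the safer dose the one that needs paperwork.

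A second reply is that the wording presupposes a last dose above 240 mg. That was probably the intention. The text does not say so, and a site follows the text.

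A third reply is partly right. With 30 mg steps, any 210 mg dose reached by reduction was preceded by 240 mg, so one tolerated cycle at 210 mg already permits a return to 240 mg. Setting those cases aside removes the 300 mg level, whose only dose below 240 mg is 210 mg. The levels 180, 210, 240 and 270 mg remain (4 of 7), with last doses of 180 or 150 mg, or 210 mg by assignment.

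A fourth reply is that subjects on a low dose by assignment have not shown intolerance, and the protocol supports 240 mg as a starting dose. That support is no DLTs in 3 evaluable subjects, together with a 300 mg single-agent MTD. For 0 of 3, the exact two-sided 95% upper limit is 1 − 0.025^(1/3) = 71%. This is thin evidence, and it does not address subjects already reduced for toxicity.

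Finally, the May 2014 count says little about who is on treatment under Amendment 4. That is correct: the current number at risk is unknown and may be zero.

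**Conclusion.** The concern holds. As written, Section 6.4.1.6 restarts a 2/7 subject last on 210, 180 or 150 mg at a dose 14%, 33% or 60% higher, and the following step up is a decrease. The clearest cases are last doses of 180 and 150 mg, and 210 mg by cohort assignment. At 210 mg after a reduction, the rule conflicts with the re-escalation condition only if that dose had not been tolerated for a cycle.

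The conclusion assumes that a site or monitor who allows treatment to resume follows the written dose without seeking an exception. Frequency is low and cannot be estimated from the documents. The point does not affect the endpoints or the analysis. It should be fixed because a safety rule gives the wrong result for doses the protocol itself permits.

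**What to change.** Reword Section 6.4.1.6 so that 2/7 subjects who miss more than 4 weeks restart at the lower of 240 mg and their last dose before the gap, and step up after one cycle only if that last dose was above 240 mg. Last doses of 150, 180 and 210 mg then restart at 150, 180 and 210 mg, and nothing changes for subjects last on 240 mg or more. The 5/14 wording can stay. The cost is one sentence, with no effect on sample size, analysis or the visit schedule.
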